3.1 General Design

The study is open label and will enroll 23 subjects (consenting up to 30 subjects).

4 Subject Selection and Withdrawal

4.1 Inclusion Criteria

Diagnosis of post Coronavirus (COVID-19)

Inclusion Criteria

a. Age ≥ 18-year-old

CONFIDENTIAL

This document is confidential and the property of the Duke University.

- b. Tested positive for SARS-CoV2
- c. Willing and able to give informed consent and adhere to visit/protocol scheduled (consent must be given before any study procedures are performed)

4.2 Exclusion Criteria

- a. Prisoners
- b. Pregnant, planning pregnancy or lactating
- c. Conditions that prohibit MRI scanning (metal in eye, claustrophobia, inability to lie supine).
- d. Medical or psychological conditions which, in the opinion of the investigator, might create undue risk to the subject or interfere with the subject's ability to comply with the protocol requirements

4.3 Subject Recruitment and Screening

Potential subjects will be identified in the Duke post-COVID clinic by clinical staff at their standard of care (SOC) at 6-12 wks. after their initial COVID-19 diagnosis. The clinical staff will focus on identifying subjects with persistent and continued dyspnea after COVID-19 infection. At initial SOC visit (post-diagnosis of COVID positive), subjects will undergo evaluation in pulmonary clinic. Pulmonary function testing (PFTs) 6-minute walk test (6MWT), and relevant labs will be ordered as indicated by the pulmonary physician. Subjects will be invited to participate in the post-COVID Pulmonary Biorepository and the COVID Long-Haulers pilot study. A subject can enroll in the COVID Long Haulers pilot without enrollment in the Biorepository.

4.4 Early Withdrawal of Subjects

4.4.1 When and How to Withdraw Subjects

A participant will be withdrawn from the study for any of the following reasons:

- Lost to follow-up.
- Withdrawal of consent.
- Death.
- If a participant is poorly compliant with study procedures, visits, and assessments, withdrawal should preferably take place after evaluation and discussion.
- If the investigator considers that continued participation in the study would be contrary to the best interests of the participant.
- Principal investigator's decision for any reason, including, but not limited to, premature termination or suspension of the study.

When a subject withdraws before completion of their study activities, the reason for withdrawal is to be documented in the eCRF and in the source document.

A subject will be considered lost to follow-up if he or she repeatedly fails to return for scheduled visits and is unable to be contacted by the study site. A subject cannot be deemed lost to follow-up until all reasonable efforts made by the study site personnel to contact the subject are deemed futile. The following actions must be taken if a participant fail to return to the study site for a required study visit:

CONFIDENTIAL

This document is confidential and the property of the Duke University.

- The study site personnel must attempt to contact the participant to reschedule the missed visit as soon as possible, to counsel the participant on the importance of maintaining the assigned visit schedule, to ascertain whether the participant wishes to or should continue in the study.
- Before a subject is deemed lost to follow-up, the investigator or designee must make every reasonable effort to regain contact with the participant (where possible, 3 telephone calls, e-mails and a certified letter to the participant's last known mailing address). These contact attempts should be documented in the participant's research records.

Should the subject continue to be unreachable, they will be considered to have withdrawn from the study.

4.4.2 Data Collection and Follow-up for Withdrawn Subjects

Participation in this study is voluntary and subjects are free to withdraw. If a subject withdraws from all study activities before the study is completed for any reason (except for death or withdrawal of consent), every attempt should be made to schedule the end of study telephone call to assess the safety and well-being of the subject. Attempts should also be made to obtain permission to record at least survival data up to the protocol-described end of subject follow-up period.

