Although the initial presentation of patients with moderate to severe symptoms of COVID19 infections is dominated by respiratory symptoms, 10% go on to develop persistent post-infection symptoms which are thought to have an inflammatory etiology. Evidence suggests that pathologic activation of the inflammasome persists beyond the acute initial presentation that contributes to the persistent disabling symptoms characterized as “long-haul COVID”. For this trial, subjects will be eligible for enrollment if they are outpatients with a history of a laboratory confirmed diagnosis of COVID-19 infection, and after 60 days or longer. We will enroll 13 subjects who continue to have respiratory symptoms (i.e., cough, shortness of breath, dyspnea on exertion). An additional 10 subjects engaged in competitive sports and diagnosed with COVID-19 will also be enrolled. These subjects can be asymptomatic or mildly to moderately. Although rare, cardiac impairment has been documented in <2% of these

CONFIDENTIAL

This document is confidential and the property of the Duke University.

individuals. To our knowledge, XeMRI has not yet been studied in this specific patient subset.

The 6-minute walk test and PFTs will not be used to guide enrollment, but rather will be used in combination with XeMRI/cMRI to assess degree of functional impairment. We will stratify our results based on ethnicity and spirometric abnormalities from those subjects without these findings.

Existing data highlight significant racial and ethnic disparities with historically underserved minority populations (i.e., Black, LatinX) suffering disproportionately higher infection rates and more severe illness compared to Whites. This is reflected by the population enrolled in our RedCAP database and biorepository. As such 30% of subjects enrolled will be required to be from underserved communities.

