2.1 Primary Study Aims

- Aim 1 - Determine the cardiopulmonary structure-function abnormalities that characterize early phase COVID-19 recovery. We anticipate conducting ¹²⁹Xe and cardiac MRI in 13 recovering COVID patients recruited at their clinic visit 60 days' or longer post-discharge from their acute infection. We will recruit patients with new onset persistent and continued dyspnea and to characterize the interstitial, pulmonary vascular and myocardial abnormalities relative to a control population.
- Aim 2 – Characterize the evolution of cardiopulmonary abnormalities over 9 months. Patients will undergo repeat scanning 9 months later to assess changes in all regional parameters acquired from pulmonary and cardiac MRI, directly addressing the possible reversibility of cardiopulmonary limitations arising from “long COVID.”
- Aim 3 – Identify MRI features that predict physiologic outcomes and can alter treatment decisions. Patients will undergo PFTs and quality of life evaluations at 3, 6 and 9 months, as well as detailed clinical histories. These data will be used to understand which baseline imaging features are predictive of long-term quality of life and physiology outcomes as well as those that represent “treatable traits” that can be targeted for therapeutic intervention.

3 Study Design

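### After withdrawal, Section 4.4.2 asks for a safety call and, as a minimum, survival, but not for the later outcomes that Aim 3 needs, so Aim 3 rests largely on completers

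*Combined protocol and SAP*

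**What the plan says.** Section 4.4.2 covers subjects who stop all study activities early. Unless the reason is death or withdrawn consent, "every attempt should be made to schedule the end of study telephone call to assess the safety and well-being of the subject". It then adds: "Attempts should also be made to obtain permission to record at least survival data up to the protocol-described end of subject follow-up period". It names no other data to pursue.

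Section 4.4.1 lists the grounds for withdrawal. One of them reads: "If a participant is poorly compliant with study procedures, visits, and assessments, withdrawal should preferably take place after evaluation and discussion". The same section requires staff to reschedule missed visits, counsel the subject and make repeated contact attempts before declaring a subject lost.

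Section 4.4.3 uses the data already collected on a withdrawn subject, and recruits a replacement so that 23 subjects complete everything.

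Aim 3 in Section 2.1 is to "Identify MRI features that predict physiologic outcomes and can alter treatment decisions". Its data are described as follows: "Patients will undergo PFTs and quality of life evaluations at 3, 6 and 9 months, as well as detailed clinical histories". The stated purpose is to learn which "baseline imaging features are predictive of long-term quality of life and physiology outcomes". The walk test is not named in Aim 3. It enters through Section 2: "The 6-minute walk test and PFTs will not be used to guide enrollment, but rather will be used in combination with XeMRI/cMRI" to gauge functional impairment.

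The schedule in Section 6.2 and the visit list in Section 6.2.3 mark lung function testing and the walk test at 6-9 months as standard of care. Section 7.2 gives no method for missing outcomes.

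**The concern.** The plan already has staff ask a departing subject for permission to keep recording something, but the one item it names is a variable that no analysis uses. The outcomes that Aim 3 does use are not requested, although some of them may be produced in ordinary clinic care.

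The retained baseline data do not repair this. Aim 3 needs pairs: a baseline imaging feature and a later outcome in the same subject. A subject who leaves after the baseline scan supplies half a pair. Replacement restores the count of 23 but not the outcome of the person who left.

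People may leave because they have become too breathless to lie in a scanner, or because they feel recovered. Either reason is plausibly related to the physiology that Aim 3 tries to predict. If so, the association between imaging and outcome is estimated in a selected group. Permission has to be sought at the time, so an analyst cannot fill the gap afterwards.

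**Working it through.** **1. The plan's own sample size (Section 7.1).** Inputs: difference 10 points, SD 10 points, power 90%, two-sided. Alpha is not stated; 0.05 is assumed. Normal approximation: n = 2 × (1.960 + 1.282)² × (10/10)² = 21.01, so 22 per group. With the t distribution, power is 89.97% at 22 and 91.2% at 23, so 23 per group is reproduced. The stated one-sided power of 99% comes out at 97.2% for 23 against 30 controls. Both figures concern the baseline comparison with healthy controls, and the present point does not depend on either.

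**2. What is needed against what is sought.**

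| Item | Used by | Sought after withdrawal (4.4.2) | Source at 6-9 months |
|---|---|---|---|
| Survival | no aim or method | yes, as a minimum | – |
| Lung function | Aim 3 | not named | standard of care |
| Quality of life | Aim 3 | not named | not in the Section 6.2 schedule |
| 6-minute walk | Section 2, functional measure | not named | standard of care |

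**3. How many subjects could be affected.** Section 3.1 allows 30 consents for 23 enrolled: 30 − 23 = 7, and 7/30 = 23.3%. Section 6.2.2 counts screen failures as withdrawn, so they use up part of the 7 and may have no baseline scan. Seven is therefore a ceiling, not an expectation. The plan gives no dropout rate.

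**4. What selective loss could do to an association (assumption: exactly the subjects with the worst outcomes are lost).** Simulated bivariate normal data, 10,000 data sets per case, 23 completers kept. The plan does not say whether Aim 3 covers all 23; that is assumed here.

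| Withdrawn | True r 0.3 | True r 0.5 | True r 0.7 | Completer mean too favourable by |
|---|---|---|---|---|
| 2 | 0.27 | 0.45 | 0.64 | 0.15 SD |
| 4 | 0.24 | 0.42 | 0.62 | 0.26 SD |
| 7 | 0.23 | 0.39 | 0.58 | 0.39 SD |

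**5. A milder assumption, for the mean only.** If leavers differ from completers by 0.5 to 1.0 SD (assumed), the shift in the completer mean is share × difference. For 7 of 30: 0.233 × 0.5 = 0.12 SD and 0.233 × 1.0 = 0.23 SD. For 3 of 26: 0.115 × 0.5 = 0.06 SD and 0.115 × 1.0 = 0.12 SD. This does not measure bias in an association, which is what Aim 3 estimates.

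**6. If leaving is unrelated to outcome.** There is no such bias, and only information is lost. For r = 0.5, arctanh(0.5) = 0.549 with standard error 1/√(n − 3). The 95% interval is 0.11 to 0.76 at n = 23 and 0.17 to 0.73 at n = 30. In general √(23/30) = 0.876, so standard errors would be about 12% smaller. That is an upper bound on the gain: it needs no screen failures and a retrievable outcome for all seven.

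**The case against.** Several points on the other side stand.

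- Survival is worded as a floor. A reader might infer that the plan forbids anything more; it does not. It simply requests nothing more.
- A reader might infer that declining the second MRI ends all outcome collection. The documents do not say so. Section 4.4.2 applies to subjects who leave everything, and Section 4.4.1 puts rescheduling, contact attempts and discussion first. What remains is that 4.4.1 does not distinguish a missed scan from leaving the study.
- A reader might infer that most of the missing outcomes sit in the chart. The documents do not show this. Section 6.2.3 says only that the data may be collected, Sections 4.3 and 6.1 have the initial tests done as clinically indicated, and the ten athletes in Section 2 can be without symptoms. A subject who cannot be reached cannot newly give permission.
- There is a larger gap upstream. Section 7 has no Aim 3 model, and the schedule has no 3-month visit and no quality-of-life item even for completers. Extra data would feed an analysis that is not yet specified.
- This is a single-site pilot with a feasibility objective, and no stated sample size or power changes.

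These points limit the size and certainty of the problem. They do not remove it: the plan names no Aim 3 outcome to pursue after withdrawal. Nor does asking about well-being by telephone amount to a quality-of-life measurement.

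**Conclusion.** The point holds as a cheap improvement to the follow-up rule. For subjects who leave entirely, other than by death or withdrawn consent, the plan names a safety call and survival and does not seek the later lung function, quality of life or walk results. Aim 3 then rests largely on completers; the exception is anyone whose later outcome was recorded before leaving.

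The size of any bias cannot be stated. It depends on how many leave after a baseline scan (at most 7, fewer if there are screen failures) and on whether leaving is related to outcome. The fall from a correlation of 0.5 to about 0.39 is an extreme case resting on the assumption that the seven worst outcomes are lost; with leaving unrelated to outcome the bias is nil. The documents do not support claiming that 30 subjects rather than 23 would be available for Aim 3.

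**What to change.** Reword Section 4.4.2 along these lines, with matching consent text:

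> At withdrawal, permission will be sought to record from the medical record, to the end of the 6-9 month window, any standard-of-care lung function test with DLCO, any 6-minute walk test, and survival. Quality of life will be collected during the end-of-study call.

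The quality-of-life instrument has to be named, since the plan names none.

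In Section 4.4.1, state that a subject who misses or declines a scan without withdrawing consent is recorded as missing that scan and stays in non-MRI follow-up. Reconcile this with the target in Section 4.4.3 of 23 subjects who complete everything.

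In Section 7.2, state that the Aim 3 analysis includes every subject with a baseline scan and a later outcome, say how missing outcomes are handled, and report how many subjects left with and without an outcome.

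The cost is a few sentences, the consent wording, a few quality-of-life questions at a call the plan already asks for, and chart review for at most about 7 subjects, some of whom will have no test on file. No visit or procedure is added, and no sample size or power figure changes.

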4.4.3 Replacement of Early Complete Withdrawal(s)

Subjects who withdraw from the study prior to completing study activities will have the data collected about them used in the primary and secondary endpoint analyses. A new subject will be consented to replace the one withdrawn to ensure data analysis of 23 subjects who have completed all interventions and completed end of study.

5 Standard of Care drugs

Subjects will take their standard of care medication during the necessary time points in the study. There will be no restrictions on concomitant medications.

6 Study Procedures

6.1 Study Visits

Potential subjects will be identified in the Duke Post-COVID at their SOC visit after their initial COVID-19 diagnosis. At the subject initial SOC visit, if indicated, subjects may undergo SOC pulmonary function testing, 6-minute walk test, laboratory blood testing, chest X-ray and cardiac MRI. Subjects will undergo ¹²⁹Xe MRI at the baseline visit and ¹²⁹Xe MRI and cardiac MRI at the 6-9-month visit.

CONFIDENTIAL

This document is confidential and the property of the Duke University.

6.2 *Scheduled of Event*

1 For women of childbearing will be performed prior to The test must be negative will be conducted and who have completed Duke Office of Clinical

2 An MRI screening form will session and verified before MRI is performed on a session, the subject will need form for each imaging

3 The ¹²⁹XeMRI session will be MRI scanner. Hyperpolarized the study team. During MRI professional (MD, DO, PA, to monitor subjects during related to Xenon MRI.

4 The Cardiac MRI session will Cardiovascular Magnetic

5 Based on the known additional effects are released from the imaging

6⁷. These procedures are considered the standard of care

8 The Research Cardiac MRI will be conduct during visit 2, will use Dotarem (IV contrast) 0.15 mmol/kg.

Protocol Activities	SOC Visit Baseline (V0)	SOC Visit Visit 1 (V1)
Months	Post COVID	6-9 Months
Informed Consent	X	
History re: Disease, exposure, secondary diagnoses	X	X
Medical history	X	
Concomitant Medications ⁶	X	X
Pregnancy Test (serum/urine) ¹	X	X
Pulmonary Function Testing with DLCO ⁶	X	X
Labs ⁷	X	X
6MWT ⁷	X	X
MRI Screening ² Form	X	X
Imaging Session (Cardiac MRI) ⁴	X ⁷	X ⁸
Imaging Session (¹²⁹ Xe MRIs) ³	X	X
Adverse Events ⁵		X
Standard dose CT	X	X
Vital Signs Assessment with optional noninvasive, optical Hemoglobin measurement	X	X

potential, a serum pregnancy test the cardiac and ¹²⁹XeMRI studies. before the MRI. The pregnancy test interpreted by study personnel competency training from the Research (DOCR).

be completed at the screening starting the imaging session. If an different day from the screening to complete a new MRI screen session.

conducted on the CAMRD research ¹²⁹Xe is produced and delivered by session, a qualified medical LNP, RN, RT, or MT) will be on hand MRI and note any symptoms

be conducted at the Duke Resonance Center (DCMRC). pharmacokinetics of Xenon, no expected after the subject is study.

6.2.1 Prescreening

If the subject is willing to participate in the study, the study coordinator will contact the subject by phone to prescreen the subject (screened for MRI contraindications and obtain verbal consent to schedule their consent/screening visit). Our study coordinators will approach potential subject who meet inclusion/exclusion criteria.

6.2.2 Baseline (V0) (post COVID DX)

Informed consent will contain a statement that indicates that if a subject does not qualify to continue in the research study after the end of the screening, he/she will be withdrawn from

the study. Subjects that sign consent but do not pass the screening are considered enrolled in the research study and counted as withdrawn.

- After obtaining informed consent, the following data may be collected and documented on the source (paper or subject's electronic medical record):
 - Documentation of relevant patient history and symptoms – SOC
 - Medical History (including comorbid conditions) – SOC
 - Vital signs (temperature, heart rate, blood pressure, respiratory rate, and pulse oximetry) including weight and height - SOC
 - Including optional noninvasive, optical hemoglobin measurement
 - Concomitant Medications – SOC
 - PFT's - SOC
 - 6MWTs – SOC
 - Labs- SOC
 - Chest X-ray-SOC
 - MRI Imaging -SOC
 - Cardiac MRI
 - Completion of MRI screening form - research
 - MRI Imaging session – research
 - ^{129}Xe MRI
 - Urine pregnancy test (if applicable) performed outside the 48hrs window
 - Adverse event reporting – research
 - Standard dose CT - research

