1.3 Risk and Benefits

1.3.1 Potential Risk

1. Inhalation of hyperpolarized ^{129}Xe may carry some minor risks. Xenon is a general anesthetic when breathed continuously at concentrations greater than 70% for extended periods of time. In the proposed study, Xenon will be delivered in a single breath, with alveolar concentrations below 25%. At these concentrations, subjects may experience transient effects, including dizziness, slight tingling or numbness of the extremities, nausea, smelling of flowers, or a feeling of well-being and euphoria. These effects will wane within 1-2 minutes of exhaling the Xenon and are documented in the consent forms.
2. The risks of participating in the MRI component of the study are considered minimal. MRI is a noninvasive imaging modality that involves no ionizing radiation. At the time of recruitment/consenting and again before the MRI session, all subjects will complete a standard questionnaire to screen for contraindications to MRI imaging (e.g., presence of metal in the eye).
3. There is also the potential risk of loss of confidentiality.
4. Administering HP ^{129}Xe without oxygen - This is necessary to preserve good image quality because O₂ is paramagnetic and depolarizes the HP ^{129}Xe . Therefore, ^{129}Xe is not mixed with O₂ within the dose delivery bag, but only once it is inhaled. Administration of a single anoxic 1-liter breath has been well tolerated by subjects undergoing both ^3He MRI and ^{129}Xe MRI. After a single breath, the residual oxygen in the subject's lungs is sufficient to maintain blood O₂ saturation during the breath-hold. For each subject, their blood-oxygenation will be monitored throughout the time they are in the MRI

CONFIDENTIAL

This document is confidential and the property of the Duke University.

scanner. To reduce risk, a baseline resting oxygen saturation of 90% on supplemental oxygen will be required. Furthermore, supplemental oxygen will be provided during the MRI exam, as indicated.

5. The IV contrast material that is used routinely during the cardiac MRI procedure. However, as with any foreign material in the body, whether food or medicine, there is always the risk of an allergic reaction. Allergic reactions occur uncommonly but may be severe and can result in death. Other specific risks from the contrast agent relate to leaking of the agent at the injection site and side effects or reactions to contrast agents.

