1.3.3 Standard dose CT (SDCT) Risk

SDCT is a standard medical procedure in lung imaging, widely used clinically and in research. Risks to participants are minimal. The study will involve a small amount of radiation exposure to the subjects. There will be one SDCT scan performed during the study. The scan protocol will be adjusted based on the participant weight. The average weight adult radiation dose is 4 mSv per scan, (8mSv) for the study. This compares to the US limit on radiation workers which is 50 mSv. Risk: The SDCT (lung scan) will be reviewed by a qualified person. There is a possibility that while reviewing the SDCT an incidental finding will be identified.

Managing risk: The patient will be informed about the incidental finding. With permission from the patient, the information about the incidental finding will be forwarded to the primary doctor or the patient can be referred to an appropriate doctor for further evaluation.

The patient will be provided the following information:

- An incidental finding may cause you to feel anxious.
- Since an incidental finding will be part of your medical record, it may affect your current or future life or health insurance coverage. This risk will vary depending on the type of insurance plan involved.

CONFIDENTIAL

This document is confidential and the property of the Duke University.

- The costs for any care that will be needed to diagnose or treat an incidental finding would not be paid for by this research study. Any additional tests or treatments will be your choice; you or your insurer will be responsible for additional costs.

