6.2.3 Visit 1 (V1) (6-9 months)

The following data may be collected and documented on the source (paper or subject's an electronic medical record):

- Documentation of relevant patient history and symptoms – SOC
- Medical History (including comorbid conditions) – SOC
- Vital signs (temperature, heart rate, blood pressure, respiratory rate, and pulse oximetry) including weight and height - SOC
 - Including optional noninvasive, optical hemoglobin measurement
- Concomitant Medications – SOC
- PFT's - SOC
- 6MWTs – SOC
- Completion of MRI screening form - research
- MRI Imaging session – research
 - Cardiac MRI
 - ^{129}Xe MRI
- Serum Pregnancy testing for a female of childbearing potential - research
 - Urine pregnancy test (if applicable) performed outside the 48hrs window
- Adverse event reporting – research
- Standard dose CT - research

CONFIDENTIAL

This document is confidential and the property of the Duke University.

7 Statistical Plan

7.1 *Sample Size Determination*

Power calculation: Based on the ^{129}Xe MRI metrics from our study (Wang, et al., 2019), we expect that we could detect an absolute difference of high barrier uptake of 10% between the post-COVID subjects and an existing cohort of healthy controls. We assume that with a standard deviation of 10% high barrier uptake within patients, and requiring a power of 90%, that a two-sided test would require a sample size of 23 to detect a difference. However, given that high-barrier uptake is expected only in the post-COVID group, a one-sided test suggests the proposed sample size has 99% power to detect a significant difference.

7.2 *Statistical Methods*

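### The negative pregnancy test is a stated condition for the MRI but not for the research CT at either visit, and section 1.3.3 counts one CT where two are scheduled

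*Combined protocol and SAP*

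**What the plan says.** **CT.** Both visit lists, 6.2.2 for V0 and 6.2.3 for V1, contain the line "Standard dose CT - research". The schedule of events in 6.2 marks the CT at both visits.

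**Pregnancy testing.** The schedule marks a serum or urine test at both visits, and 4.2 excludes women who are pregnant, planning pregnancy or lactating. The V1 list has "Serum Pregnancy testing for a female of childbearing potential - research", with a urine test beneath it. The V0 list prints only the urine line: "Urine pregnancy test (if applicable) performed outside the 48hrs window".

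**The condition.** Footnote 1 of 6.2 is split across two columns in the text as read from the PDF. The left part runs "For women of childbearing will be performed prior to The test must be negative" and the right part has "a serum pregnancy test the cardiac and ¹²⁹XeMRI studies. before the MRI". Joined line by line, it tells women of childbearing potential to have a serum test ahead of the cardiac and xenon MRI, with a negative result needed before the MRI. The rest of the note concerns who conducts and interprets the test.

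**Radiation.** Section 1.3.1 says "MRI is a noninvasive imaging modality that involves no ionizing radiation". Section 1.3.3 says the CT does involve radiation exposure and states "There will be one SDCT scan performed during the study". It then gives 4 mSv per scan for an adult of average weight and 8 mSv for the study.

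**The concern.** The protocol attaches its negative-test condition to the procedure that it describes as free of ionizing radiation, and leaves the condition off the one research procedure that delivers it. As written, a CT could be done before the pregnancy result is known without departing from any stated rule.

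V1 is where this matters most. Eligibility was checked at entry, and V1 comes 6-9 months later. Pregnancy is not named among the withdrawal reasons in 4.4.1, and no text requires contraception. Section 8.1 counts pregnancies as safety data, but reporting comes after any exposure. The V1 test is therefore the main safeguard, and it is not tied to the CT.

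The scan count matters for a different reason. Section 1.3.3 is where a reader looks up the radiation burden, and it contradicts itself on the number of scans.

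**Working it through.** **Which procedures wait for a negative test**

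| Procedure | Label | Visits | Ionizing radiation | Negative test stated as a condition |
|---|---|---|---|---|
| Xenon MRI | research | V0, V1 | no (1.3.1) | yes (6.2, footnote 1) |
| Cardiac MRI | standard of care at V0, research at V1 | V0, V1 | no (1.3.1) | yes (6.2, footnote 1) |
| Standard dose CT | research | V0, V1 | yes (1.3.3) | none found |

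The chest X-ray in 6.2.2 is standard of care, so the CT is the only research-labelled procedure that uses ionizing radiation.

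**Whether another passage supplies the condition for CT**

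- Section 4.2 excludes pregnancy at entry. With the V0 test in the schedule, this covers eligibility, but it does not say that the CT waits for the result.
- Section 1.3.3 covers dose and incidental findings. It has no pregnancy precaution.
- The order of the lists does not settle it. Both lists print the CT after the pregnancy test, but both also print the MRI before the test that must precede it. Print order therefore cannot be the intended order of procedures.

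**Scan count**

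Inputs: 4 mSv per scan and 8 mSv for the study (1.3.3); one CT at V0 and one at V1 (6.2, 6.2.2, 6.2.3).

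- Reproducing the plan's total: scans × dose per scan = 2 × 4 mSv = 8 mSv. This equals the printed total.
- Scans implied by the printed total: 8 / 4 = 2. This equals the schedule.
- Using the printed count: 1 × 4 mSv = 4 mSv. This does not equal the printed total.

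The schedule, both visit lists and the total agree on two scans. Only the count sentence disagrees. If one CT were really intended, the total would have to become 4 mSv and one CT would have to come out of the schedule and out of 6.2.2 or 6.2.3.

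**The case against.** The strongest reply is that protection is already largely in place. Pregnant women and those planning pregnancy are excluded, subjects who do not pass screening are withdrawn, and a test is scheduled at each visit. In the schedule the CT row sits below the test row. Nothing suggests that anyone plans to scan before testing. Harm would need an undetected pregnancy and also a CT done ahead of a test that is already due. All of this stands, and it limits the point to a missing condition and a missing order, mainly at V1. It does not remove the point, because the protocol chose to state the condition explicitly for MRI and did not do so for CT.

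A reader might infer more than the documents support:

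- *That the CT is given without pregnancy testing.* It is not; tests are scheduled at both visits.
- *That V0 uses only a urine test.* The V0 list omits the serum line, but footnote 1 and the schedule row cover serum testing there. The urine line stands alone in 6.2.2 and beneath a serum line in 6.2.3, which suggests that a line was dropped.
- *That the CT may fall on another day.* Footnote 2 of 6.2 speaks of an MRI on a "different day from the screening" session, and concerns repeating the MRI screening form. It says nothing about when the CT is done.
- *That the radiation dose is understated by half.* The printed 8 mSv is correct for two scans. The consent pages are not available, so what subjects are told cannot be judged.
- *That the number of women at risk can be estimated.* The documents do not give the number of women of childbearing potential, or any fetal dose.

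The protocol does not say what the CT is for. That is a separate question and adds nothing to this one.

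**Conclusion.** The point holds on two items, and both should be corrected.

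First, the negative-test condition covers the cardiac and xenon MRI and omits the research CT at V0 and V1. At V0 the entry exclusion and the scheduled test leave little beyond an unstated order. At V1 a test is scheduled, but nothing makes a negative result a condition for the CT, and eligibility was checked 6-9 months earlier. No count of affected women and no fetal dose can be given.

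Second, the scan count in 1.3.3 is one and should be two. The total of 8 mSv is right. This part is editorial, although it sits in the radiation-risk section.

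The conclusion assumes that footnote 1 has been correctly rejoined across its columns (every legible part names MRI only), that two CTs are intended, and that the stated 4 mSv applies to each scan. No planned comparison, sample size or error rate is affected.

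**What to change.** 1. In footnote 1 of 6.2, require the pregnancy test already scheduled at each visit to be done and negative before the CT as well as before the cardiac and xenon MRI. Add the matching precaution to 1.3.3.
2. In 1.3.3, change the count to two scans, one per visit, at 4 mSv each and 8 mSv in total.

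Restoring the serum line in the V0 list would be a helpful tidy-up in the same edit. No time window is proposed, because the protocol refers to a 48-hour window without defining it.

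The cost is a few lines of text, an ordering constraint within each visit, and a possible repeat test if CT and MRI fall on different days. The sample size and the xenon analysis stay as they are.
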